## 2.7. Imputation of Missing Data

Unless specified otherwise, no data imputation will be applied for missing safety and efficacy evaluations. For analysis and reporting purpose, partial dates in adverse event (AE onset date; AE end date), concomitant therapies (start date; end date), MM diagnosis date, and start date of subsequent anticancer therapy will be imputed.

### 2.7.1. Adverse Event Start and End Date

#### Adverse Event Start Date

If the onset date of an adverse event is completely or partially missing, the following imputation rules will be used.

- When month and year are present and the day is missing:
  - If the onset month and year are the same as the month and year of first dosing date, the day of first dosing or the day-component of the AE end date (possibly imputed) is imputed, whichever is earlier;
  - If the onset month and year are not the same as the month and year of first treatment with study drug, the first day of the month is imputed.
- When only a year of the onset date is present:
  - If the onset year is the same as the year of first treatment with study drug:
    - If AE end date is available and is prior to first dosing date, the day and month of AE end date are imputed;
    - Otherwise, the day and month of the first dosing date are imputed.

- If the onset year is different from the year of first treatment with study drug, the 1st of January is imputed.
- If the onset date is completely missing, the first dosing date is imputed as the onset date.

No imputation will be done for partial or missing AE onset time.

### Adverse Event End Date

If the end date of an adverse event is completely or partially missing, the following imputation rules will be used.

- If month and year are present and the day of the month is missing, the last day of the month is imputed.
- If only a year is present, the 31st of December is used.

After the imputation, if the imputed date is later than the date of death (if available) after imputation, the date of death will be used as the imputed date.

No imputation will be done for partial or missing AE end time.

### **2.7.2. Prior and Concomitant Medication/Therapy Start and End Date**

For prior or concomitant medications/therapy, if the start or end date is completely missing, no imputation will be performed. If the start or end date is partially missing, the following imputation rules will be used.

- If only the day is missing, the 15th day of the month will be used.
- If both the day and month are missing, the 30th of June will be used.

If the medication/therapy was taken prior to study start, and the imputed start date is after first dosing date, further adjust the imputed start date as the day prior to first dosing date; if the medication/therapy was taken after study start, and the imputed start date is prior to first dosing date, further adjust the imputed start date as first dosing date. Also adjust the imputed medication/therapy end date so that it is on or after first dosing date.

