#### **4.5. Prior and Concomitant Medications**

Medications administered prior to the first dose date of study drug will be considered as prior medications. Concomitant medications are defined as those medications taken on or after the first dose date through 30 days after the last dose date.

Prior medications will be summarized on ITT analysis set by therapeutic class, pharmacologic class, and preferred term.

Concomitant medications will be summarized on safety analysis set by therapeutic class, pharmacologic class, and preferred term. Similar summaries will be provided for subjects who received concomitant growth factor support, systemic steroids, antiviral systemic use, and prophylactic antiviral medications during the study, respectively.

Pre-dose medications and post-dose medications will also be summarized by therapeutic class, pharmacologic class, and preferred term, respectively.

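### SAP Section 2.7.2 does not limit its end-date adjustment to drugs taken after study start, so a drug stopped before first dose with a partial stop date can be tabulated as concomitant

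*SAP*

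**What the plan says.** SAP Section 2.7.2 sets one rule for prior and concomitant records together. Completely missing dates stay missing: "For prior or concomitant medications/therapy, if the start or end date is completely missing, no imputation will be performed". For partial dates, start or stop, it says: "If only the day is missing, the 15th day of the month will be used". And: "If both the day and month are missing, the 30th of June will be used".

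Three adjustments follow.

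- Start date, first case: "If the medication/therapy was taken prior to study start, and the imputed start date is after first dosing date", the start becomes the day before first dose.
- Start date, second case: "if the medication/therapy was taken after study start, and the imputed start date is prior to first dosing date", the start becomes the first dosing date.
- End date, in a sentence of its own: "Also adjust the imputed medication/therapy end date so that it is on or after first dosing date".

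SAP Section 4.5 then classifies the records. On one side: "Medications administered prior to the first dose date of study drug will be considered as prior medications". On the other: "Concomitant medications are defined as those medications taken on or after the first dose date through 30 days after the last dose date". It plans separate summaries of concomitant growth factors, systemic steroids and antivirals.

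**The concern.** The start-date adjustments make an imputed date agree with what is known about when the drug was taken. The end-date sentence, taken at face value, does so only for drugs still in use at first dose. For a drug known to have stopped earlier it does the reverse: it replaces a stop before first dose with one on or after it. Because Section 4.5 defines concomitant use by timing relative to first dose, the drug would enter the concomitant tables although the subject was no longer taking it. It would also remain a prior medication, so it would be counted in both places.

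Section 2.7.2 also does not check an imputed stop against a known start, or an imputed start against a known stop. Neighbouring rules do make this kind of check: Section 2.7.1 looks at the adverse event end date when imputing the onset, and Section 2.7.4 looks at the stop date of the subsequent therapy when imputing its start.

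**Working it through.** The plan gives no figure to reproduce, so the check applies the rule to dated examples. The dates are illustrative assumptions: first dose 20 March 2018 and last dose 1 September 2018 unless stated. The Section 4.5 concomitant window then runs from 20 March to 1 October 2018 (1 September + 30 days).

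**Which records can be reached.** Protocol Section 8 collects the listed concomitant drug classes from consent onward. Screening lasts up to 28 days before randomization (Protocol Section 3.1), and treatment should start within 72 hours after it (Protocol Section 9.1.3). Consent to first dose is therefore at most about 28 + 3 = 31 days, here from 17 February 2018. The exposed records are drugs stopped in that interval with a partial stop date. Complete stop dates are not imputed, so the rule leaves them alone.

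**Literal reading (the end-date sentence applies to every record).**

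| Start | Recorded stop | Imputed stop | After the end-date sentence | Section 4.5 |
|---|---|---|---|---|
| 25 Feb 2018 | Feb 2018 | 15 Feb 2018 | 20 Mar 2018 or later | prior and concomitant |
| 20 Feb 2018 | Mar 2018, before first dose | 15 Mar 2018 | 20 Mar 2018 or later | prior and concomitant |

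In the first row the true stop lies between 25 and 28 February, so the derived stop is at least 20 days late. In the second it lies between 1 and 19 March, so the derived stop is at least 1 day late. With the end-date sentence limited to drugs taken after study start, the end dates stay at 15 February and 15 March and neither record is concomitant. The 15 February date is still wrong, because it is 10 days before the known start.

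**Narrow reading (the sentence applies only to drugs taken after study start).** The imputed start of a prior drug is capped at the day before first dose, but its imputed end is not.

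- Stop recorded as 2018, drug stopped before 20 March: the stop is imputed to 30 June 2018. That is 11 + 30 + 31 + 30 = 102 days after first dose and inside the window, so the drug is concomitant.
- First dose 10 March 2018, stop recorded as March 2018, true stop 1 to 9 March: the stop is imputed to 15 March, 5 days after first dose, so the drug is concomitant. This happens whenever first dose falls on or before the 15th and the drug stopped earlier in the same month.

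**Date order.** A start of 20 June with a stop recorded as June gives 15 June, 5 days before the start. Under the narrow reading nothing corrects this unless the imputed stop also falls before first dose for a drug taken after study start.

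**The case against.** The best defence is that the end-date sentence opens with a connecting word and directly follows the clause on drugs taken after study start. Read as a continuation, it is sensible: with first dose on 20 June, a drug started and stopped in June after first dose is imputed to 15 June at both ends, and both ends need to move to 20 June. This is probably what was meant. It is also fair that both start-date clauses presume the before-or-after status is already known, and that the SAP nowhere says an imputed end date overrides that status. But it does not say the status overrides the dates either, and no other section exempts prior drugs. The narrow reading also leaves the missing cap and the date-order fault in place.

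The impact is small, and that part of the defence stands. Every subject receives a corticosteroid before each dose (Protocol Section 6.3.1) and antiviral prophylaxis is recommended (Protocol Section 8.1.4). To the extent that those are counted in the steroid and antiviral summaries, a few screening-period records would change the percentages little.

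A reader might infer more than the documents support:

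- **Therapies finished years earlier would fill the concomitant tables.** Only prestudy antineoplastic and myeloma therapies are recorded from before consent. SAP Section 4.4 summarizes prior myeloma therapy separately, by exposure, number of lines and refractory status from the case report form, none of which uses an end date.
- **Moved end dates would create false washout or prohibited-therapy deviations.** SAP Section 4.8 lists deviation types but does not derive them from imputed dates, and the sponsor reviews key eligibility criteria before randomization (Protocol Section 4).
- **All affected records are misclassified, so the problem is large.** Under the literal reading every drug stopped before first dose with a partial stop date does become concomitant, but that follows from how the group is defined and says nothing about how many there are.

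**Conclusion.** The point holds as a fault in a stated derivation rule. Section 2.7.2 covers prior drugs, and its end-date sentence carries no restriction to drugs taken after study start. The literal reading misclassifies any drug stopped between consent and first dose whose stop date is partial. The narrow reading still does so when the imputed 15th or 30 June falls on or after first dose. Under either reading an imputed date can contradict a known one.

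The consequence is limited to the descriptive concomitant-medication tables of SAP Section 4.5. ORR, maximum trough concentration and the four hierarchical secondary tests do not use these dates. The start of subsequent anticancer therapy, which does bear on response and PFS, has its own rule in Section 2.7.4. The documents give no rate of partial stop dates, so the number of affected records cannot be estimated. The conclusion assumes that concomitant status is derived from the imputed dates. If a recorded flag decides it instead, the classification error disappears, but the SAP does not say so.

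**What to change.** Replace the end-date sentence in SAP Section 2.7.2 with three rules:

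1. Move an imputed end date up to first dose only for drugs taken on or after first dose, or ongoing at first dose.
2. If a drug was stopped before first dose and its imputed end falls on or after first dose, set the end to the day before first dose.
3. If an imputed end falls before a known start, set it to the start date. If an imputed start falls after a known end, set it to the end date.

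These rules need the same before-or-after status that the start-date adjustments already rely on. Where the recorded stop month and year precede those of first dose, the partial date settles it. The cost is a short SAP edit and one programming derivation.

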### **2.7.3. Multiple Myeloma Diagnosis Date**

If the diagnosis date of multiple myeloma (MM) is completely missing, no imputation will be applied. If the diagnosis date is partially missing, the following imputation rules will be applied:

- If only the day of the diagnosis date is missing:
  - If the month and year of the diagnosis date are the same as the month and year of the start date of the first line of prior MM therapy, and day of the start date of the first

- line of prior MM therapy is available, impute day of the diagnosis date with the day of the start date of the first line of prior MM therapy;
- Otherwise, impute day of diagnosis date with 15;
- If both month and day of the diagnosis date are missing:
    - If the year of the diagnosis date is the same as the year of the start date of the first line of prior MM therapy, and the month of the start date of the first line of prior MM therapy is available:
      - if both month and day of the start date of the first line of prior MM therapy are available, impute diagnosis month and day with the month and day of the start date of the first line of prior MM therapy;
      - if only the month of the start date of the first line of prior MM therapy is available, impute the month of diagnosis date with the month of the start date of the first line of prior MM therapy and the day of the diagnosis date with 15;
      - Otherwise, impute the month and day of the diagnosis date with June 30.

#### **2.7.4. First Subsequent Anticancer Therapy Start Date**

If the start date of the first subsequent anticancer therapy is completely missing or the month is missing, no imputation will be performed. If only the day of the first subsequent therapy start date is missing, the following imputation rules will be applied:

- If the month and year of the start date are the same as the month and year of the last dosing date, the day of last dosing date +1 or the day-component of the stop date of subsequent anticancer therapy will be imputed, whichever is earlier.
- If the month and year of the start date are not the same as the month and year of last dosing date, the first day of the month will be imputed.

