9.2. Efficacy Evaluations

9.2.1. Response Categories

Disease evaluations must be performed every 28 days (± 7 days), regardless of any changes to the dosing regimen, until disease progression. Disease evaluations will be performed by a central laboratory (unless otherwise specified). This study will use the IMWG consensus recommendations for multiple myeloma treatment response criteria (Durie 2006⁷; Kumar 2016¹¹; Rajkumar 2011²²) presented in Table 5. For quantitative immunoglobulin (QIg), M-protein, and immunofixation measurements in serum and 24 hour urine, the investigator will use results provided by the central laboratory. For subjects with light chain multiple myeloma, only serum FLC assay will be performed routinely. Otherwise, serum FLC assay test results will be analyzed by the central laboratory only for the assessment of sCR. For subjects with suspected daratumumab interference on serum M-protein quantitation by electrophoresis (SPEP) and immunofixation, a reflex assay will be performed (Attachment 10). Subjects with confirmed daratumumab interference who meet all other clinical criteria for CR or sCR will be considered CR/sCR.

Table 5: International Uniform Response Criteria Consensus Recommendations

Response	Response Criteria
Stringent complete Response (sCR)	
 CR as defined below, plus Normal FLC ratio, and Absence of clonal PCs by immunohistochemistry, immunofluorescence^a or 2- to 4-color flow cytometry
Complete response (CR)*	
 Negative immunofixation on the serum and urine, and Disappearance of any soft tissue plasmacytomas, and <5% PCs in bone marrow
Very good partial Response (VGPR)*	
 Serum and urine M-component detectable by immunofixation but not on electrophoresis, or $\geq 90\%$ reduction in serum M-protein plus urine M-protein <100 mg/24 hours

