**Table 2: PFS Event and Censoring Method**

Situation	Date of Progression or Censoring	Outcome
No postbaseline disease assessment	Randomization	Censored
Disease progression at or prior to start of subsequent anticancer therapy	Earliest date that indicates disease progression	PFS event
Death at or prior to start of subsequent anticancer therapy	Date of death	PFS event
Other, such as: Withdrawal of consent to study participation, Lost to follow-up Start of subsequent anticancer therapy prior to disease progression or death	Date of last disease assessment prior to withdrawal of consent to study participation, lost to follow-up, or start of subsequent anticancer therapy	Censored

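### SAP 2.7.4, followed literally, compares day numbers without checking the month of the stop date, so it can date next therapy before the last study dose; a full-date comparison was probably meant and should be stated

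*SAP*

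**What the plan says.** SAP 2.7.4 imputes a missing start day for the first subsequent anticancer therapy. If the month and year match those of the last dose, the candidates are the day of last dose plus one, "or the day-component of the stop date of subsequent anticancer therapy will be imputed, whichever is earlier". If the month differs, the first of the month is used and the stop date plays no part.

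The date is then used as follows:

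- **Time to next therapy (SAP 5.3.4.1):** it is the event date.
- **PFS (SAP Table 2):** a progression is an event only under the condition "Disease progression at or prior to start of subsequent anticancer therapy", and it is dated by the "Earliest date that indicates disease progression". Otherwise the subject is censored at the last disease assessment before next therapy.
- **Duration of response (SAP 5.3.7.1):** it sets the censoring point when next therapy starts without progression.
- **Treatment-emergent adverse events (SAP 6.1):** it can close the reporting window.

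Neighbouring rules do check the month or the full date:

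- SAP 2.7.3 borrows a day only under a match: "If the month and year of the diagnosis date are the same as the month and year of the start date" of first prior therapy.
- SAP 2.7.2 adds a correction when "the imputed start date is prior to first dosing date, further adjust the imputed start date as first dosing date".
- The year-only rule in SAP 2.7.1 tests the whole date: "If AE end date is available and is prior to first dosing date".

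The day-missing rule in SAP 2.7.1 has the same weakness as 2.7.4: "the day of first dosing or the day-component of the AE end date (possibly imputed) is imputed, whichever is earlier".

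**The concern.** Month and year are already known when 2.7.4 applies, and the text names a day-component. A programmer who follows the words takes the smaller of two day numbers and places it in the start month. If the stop falls in a later month, its day number says nothing about when therapy began, yet a small one wins. No floor at the last dose catches the result.

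A progression dated between the false start and the last dose then appears to follow next therapy and is censored. PFS is second in the tested hierarchy (SAP 5.1.1). Treatment continues until progression is confirmed (Protocol 10.1), so a progression dated shortly before the last dose is an ordinary sequence. Two programmers could code the sentence differently and both claim to follow it.

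**Working it through.** The plan gives no figure here to reproduce, so the check applies the rule itself.

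**Two readings.** Literal: imputed day = min(day of last dose + 1, day of stop), placed in the start month. Full-date: imputed date = min(last dose + 1 day, stop date).

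**Worked case (illustrative dates).** Last dose 20 June, start in June with the day missing, stop 5 September.

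- Literal: min(20 + 1, 5) = 5, so 5 June, which is 20 − 5 = 15 days before the last dose.
- Full-date: min(21 June, 5 September) = 21 June.
- Suppose obvious radiographic progression is dated 18 June; Protocol 9.2.6 needs no repeat x-ray. Against 21 June it is a PFS event. Against 5 June it is censored.

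**When it misfires.** I took every last-dose day in 2018 with every stop from that day to 365 days later: 365 × 366 = 133,590 pairs.

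| Stop date | Pairs | Literal date before last dose |
|---|---|---|
| Same month as last dose | 5,738 | 0 |
| Later month | 127,852 | 64,451 (50.4%) |

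The fault therefore needs a stop in a later month. If the stop day is spread evenly over that month, the chance for a last dose on day d is (d − 1)/30.4: 4/30.4 = 13% for day 5, 14/30.4 = 46% for day 15, 24/30.4 = 79% for day 25. These describe an assumed calendar grid and are not expected trial rates.

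**Month end.** For a last dose on 30 June, last dose plus one is either day 31, which June lacks, or 1 July, outside the recorded month. When that candidate is the one used (for example, therapy is ongoing and has no stop date), the rule gives no valid day.

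**Bound on time to next therapy.** Imputation stays within the recorded month, so the error is at most about 30 days.

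**PFS.** Protocol 9.2.1 says "Disease evaluations must be performed every 28 days" with a window of 7 days either way, and Protocol 9.2.2 requires a repeat for progression on one laboratory test. Laboratory progression confirmed at the next scheduled visit is thus first dated about 28 − 7 = 21 to 28 + 7 = 35 days before a last dose given at that visit. The table shows simulated loss of a PFS event, given a missing start day, a start in the last-dose month and a complete stop date. Gaps to next therapy and durations are assumptions; durations here are spread out (exponential or uniform).

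| Gap to next therapy | Progression 0 days before last dose | 7 days | 14 days | 21 days | 28 days |
|---|---|---|---|---|---|
| Uniform from day 1 to day 7, 14 or 28 | 31–45% | 14–25% | 5–11% | 1–2% | 0% |
| 14–28 days | 17–19% | 3–4% | about 0% | 0% | 0% |
| 28–35 days | about 2% | 0% | 0% | 0% | 0% |

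Fixed courses are fragile too. With gaps starting at day 1 and progression on the last-dose day, 28-day courses give 15–35% if stop = start + duration − 1, but 9–23% if stop = start + duration. For 84-day courses with progression 7 days earlier, the same one-day change moves the loss from 3–7% to 0%.

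**Revised rule (see fix).** On the 133,590 pairs it never gives a date before the last dose. It equals the last dose in 4,745: 4,392 from month-end last doses (12 × 366) and 353 with the stop on the last-dose day. Table 2 still counts a progression on that day.

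**The case against.** The best defence is that the sentence is shorthand. Dates are earlier; day numbers are smaller. The stop-date clause does useful work only as a cap that keeps start from passing stop, which can bind only within the same month, where no misfire occurs. Separate data presentation specifications (SAP 4.4.1) are not available, so the actual coding is unknown. This stands as a reading of intent, but intent is not a specification.

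Timing also limits the harm. Protocol 9.1.3 places the End-of-Treatment Visit 4 weeks after the last dose and asks for every effort to hold it before next therapy. With a gap of 28–35 days, only about 2% of starts share the last-dose month at all. The protocol does allow an earlier visit, so short gaps remain possible. This stands, and it is why the simulated percentages cannot serve as a size.

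For time to next therapy, any imputation within a month is imprecise. With gaps of 1–28 days, mean absolute error is about 12 days under the literal rule and about 9 under full dates. That endpoint is outside the tested hierarchy, and duration of response has no formal comparison (SAP 5.3.7.2).

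Two stronger readings are tempting. A reader might infer that the PFS comparison or the ORR co-primary is biased. The documents give no count of such records and no reason for them to differ by arm, and no change in either ratio has been shown. A reader might also infer that the matching wording in SAP 2.7.1 distorts treatment-emergent counts. SAP 6.1 treats events with partial onset dates as treatment-emergent unless onset can be determined as before first dose or later than 30 days after the last dose, so that status is largely protected. SAP 6.1 also keeps related events treatment-emergent whatever their start date, so early closure of the window through 2.7.4 mainly concerns new unrelated events.

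**Conclusion.** The point holds and is minor. As written, the rule can place next therapy before the last study dose, and it has no valid answer for some month-end last doses. Both defects follow from the text without assumptions, though a full-date comparison was probably intended and would remove the first.

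Exposure is narrow. The first defect needs a missing start day, a start in the last-dose month, and a complete stop date in a later month with a smaller day number. A PFS event is lost only if progression is also dated after the false start, which in practice means on or shortly before the last dose. The number of such records is not given and is probably small.

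PFS loss per eligible record runs from about 0–2% when next therapy follows the Week 4 visit to several tens of percent when it starts within days. That range reflects assumed gaps and durations, so no single figure should be quoted. Loss through the confirmatory sample is not claimed, because the response algorithm in SAP Attachment 2 is not in the material available.

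**What to change.** Replace the first bullet of SAP 2.7.4 with:

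> If the start month and year equal those of the last dosing date, impute the earlier of two full dates: last dosing date + 1 day, and the complete stop date of that therapy. If the earlier date falls in the next month, impute the last day of the recorded start month.

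A separate same-month condition on the stop date is unnecessary once full dates are compared. The revised rule can return the last-dose date itself. It returns an earlier date only when the recorded stop is itself before the last dose, and the data then support it.

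Aligning the day-component wording in SAP 2.7.1 is optional tidying. The cost is two sentences and a small code change. No dose, schedule or clinical rule is touched.
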